10.2 Analysis Populations

The following are the analysis populations:

- Safety Population (SAF): This is defined as all subjects who were treated for a UKA or TKA with the use of the CORI Robotics and a Smith+Nephew Knee Implant System.
- Full analysis set population (FAS): The FAS is a subset of the subjects of the SAF population who have at least one post-operative assessment on any of the effectiveness endpoints or health-related quality of life (HRQoL) endpoints.
- Per-Protocol Population (PP): The PP population is a subset of subjects in the FAS population who do not have major protocol deviations and who satisfied all enrollment eligibility criteria. Major protocol deviations will include but not only restricted to subjects enrolled who do not satisfy the study entry eligibility criteria. All other criteria that will be categorized as major deviations will be formally classified on a case-by-case basis prior to the final study database lock.

10.3 Baseline Data

All observations available prior to the operative date will be defined as baseline data. All demographic and pre-operative characteristics data will be summarized at baseline. All demographic and baseline characteristics will be summarized using the SAF, FAS and PP analysis populations.

Clinical Protocol

A Prospective, Multi-center, Study to Evaluate the Safety and Effectiveness of REAL INTELLIGENCE™ CORI™ in unicondylar knee arthroplasty (UKA) and total knee arthroplasty (TKA) procedures

Study Number: CORI.2019.07

Version: 6.0, 15/Jan/2024

Page: 56 of 122

10.4 Efficacy Analysis

10.4.1 Analysis of Primary Endpoint

Leg alignment

The primary endpoint, the proportion of knees achieving post-operative leg alignment, defined as $\pm 3^\circ$ from the target (pre-operative planned leg alignment) assessed at the 6 weeks study visit in the CORI Robotics UKA (n1) and CORI Robotics TKA (n2) groups.

The proportions as described above will be summarized along with their associated two-sided 95% confidence intervals (CIs), estimated using exact binomial methods.

The hypothesis of superiority in leg alignment in both groups will incorporate the use of the Intersection Union Test (IUT) where superiority will be inferred if and only if the outcomes from the simultaneous comparisons relative to the literature-specified rate provided of 73.4% yield lower limits of their two-sided 95% CIs both greater than 73.4% (i.e. both lower limits of the 95% CIs from the two groups must be greater than 73.4%) [52]. No multiplicity adjustments are required through the use of the IUT. The leg alignment will additionally be summarized using summary statistics for the pooled CORI Robotics UKA and CORI Robotics TKA groups (n).

As supportive analysis on the primary endpoint, the difference between the target and actual leg alignment achieved postoperatively will be summarized for each group (i.e. CORI Robotics UKA versus CORI Robotics TKA) as well as for the combined groups using summary statistics for continuous variables. Ninety-five (95) % CIs based on the Student's t-distribution will be calculated for the means.

The primary endpoint and the supportive analysis will be summarized using the FAS analysis population as primary and then PP analysis population for sensitivity.

10.4.2 Analysis of Secondary Endpoint

All analyses on the secondary endpoints will be carried out separately in the CORI Robotics UKA and CORI Robotics TKA groups.

Component Alignment

Femoral components (internal rotation, valgus and anterior tilt) and tibial components (internal rotation, valgus, and posterior slope) will be summarized using descriptive summary characteristics for continuous variables.

Clinical Protocol

A Prospective, Multi-center, Study to Evaluate the Safety and Effectiveness of REAL INTELLIGENCE™ CORI™ in unicondylar knee arthroplasty (UKA) and total knee arthroplasty (TKA) procedures

Study Number: CORI.2019.07

Version: 6.0, 15/Jan/2024

Page: 57 of 122

Standard Radiographic Assessment

Radiolucent lines (mm) by zone and visit will be summarized using descriptive statistics for continuous variables.

2011 Knee Society Score (KSS)

The 2011 KSS objective, function and satisfaction scores will be summarized at the pre-operative and postoperative visits using continuous summary characteristics. For each of these 3 KSS scores, independent repeated measures Analysis of Covariance (ANCOVA) models (to account for the correlation between subjects with bilateral knees) will be used to model the KSS scores as the dependent variable. As a minimum, each model will contain a visit (pre-operative and postoperative) and the investigational site as a fixed term with a repeated specification for the knee. Pre-operative prognostic and demographic variables not only restricted to age, BMI and sex, but that can also be ascertained to have an impact on the KSS scores will be introduced as covariates in the final model. These covariates will be added to the model using a stepwise approach and a covariate is retained in the final model if and only if it's associated p-value ≤ 0.1 . Model based means (adjusted means or Least Square Means, LSMeans) and corresponding standard errors associated with each KSS score at the pre-operative visit and postoperative visits will be presented. Model based changes (and corresponding standard errors) from the pre-operative visit to each subsequent postoperative as well as their corresponding 95% CIs will additionally be summarized. If the p-value associated with the visit term in the model is significant (i.e. $p < 0.05$), then the 95% CIs corresponding to the model based change (LS Mean) from the pre-operative to each postoperative visit will indicate where significant differences (changes) from the pre-operative at postoperative are found.

The 2011 KSS subject expectation score will be summarized at the pre-operative and postoperative follow-up visits using descriptive characteristics for continuous variables.

Oxford Knee Score (OKS)

The OKS (0-48) will be summarized at the preoperative and postoperative visits using continuous summary characteristics. The repeated measures ANCOVA model to account for the correlation between subjects in case of bilateral knees analogous to that specified for the 2011 KSS will be used.

Forgotten Joint Score (FJS)

The transformed FJS score (0-100) will be summarized at the postoperative visits using continuous summary characteristics. The repeated measures ANCOVA model to account for the correlation between subjects in case of bilateral knees analogous to that specified for the 2011 KSS will be used.

Clinical Protocol

A Prospective, Multi-center, Study to Evaluate the Safety and Effectiveness of REAL INTELLIGENCE™ CORI™ in unicondylar knee arthroplasty (UKA) and total knee arthroplasty (TKA) procedures

Study Number: CORI.2019.07

Version: 6.0, 15/Jan/2024

Page: 58 of 122

EQ-5D-5L Score

The HRQoL Index score and VAS score will be summarized using summary statistics for continuous variables pre-operatively and at all postoperative visits. In the case of bilateral knees, repeated measures ANCOVA models will account for correlation between subjects with bilateral knees each for the index score and VAS analogous to that specified for the 2011 KSS will be used.

All secondary endpoints will be summarized using the FAS analysis population.

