8.4.4 Pre-specification of Statistical Analysis

The primary outcome measure has been pre-specified as well as the type of statistical analysis to be performed in order to evaluate this outcome. The details of the analysis will further be pre-specified in the Statistical Analysis Plan (SAP) so as minimize any threats to external validity and yield clinically relevant estimates of effects and precision.

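### The PROM models in 10.4.2 let the data choose the covariates, and the adjusted visit means do not say how sites are weighted

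*Combined protocol and SAP*

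**What the plan says.** The model is set out in protocol section 10.4.2 under the 2011 KSS. Its smallest form has a visit effect, "the investigational site as a fixed term", and a repeated effect for the knee. Further pre-operative variables may enter. Age, BMI and sex are named, but the list is explicitly left open. Selection is by rule: "These covariates will be added to the model using a stepwise approach"; a variable stays only when its p-value is at most 0.1.

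Two kinds of output follow: "Model based means (adjusted means or Least Square Means, LSMeans) and corresponding standard errors associated with each KSS score" for every visit, and "Model based changes (and corresponding standard errors) from the pre-operative visit to each subsequent postoperative as well as their corresponding 95% CIs". Significance is read from the visit term and from the intervals of the changes.

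The analogous model is used for OKS, FJS and EQ-5D-5L, and every secondary analysis is run separately in the two groups. The FJS is collected only after surgery (8.3.2, Table 9-1). Raw summaries are planned beside the model for each score; for the FJS, "The transformed FJS score (0-100) will be summarized at the postoperative visits using continuous summary characteristics".

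Section 10.1 names SAS 9.3 or later. No LSMeans option or site weighting is given. Section 7.1 allows up to 8 sites for 80 subjects, with no minimum or cap per site.

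**The concern.** Two separate choices are left open.

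**Covariates.** Section 8.4.4 relies on pre-specification to protect validity. Here neither the candidate list nor the final model is fixed, and the study is non-blinded. There are four instruments, with KSS contributing three modelled scores and EQ-5D-5L two, and each is modelled in two groups. Each model could end with a different adjustment set for reasons of chance, and the reported standard errors would ignore the selection.

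**Site weights.** An LSMean from a model with a site factor is a weighted average over sites, so the weights define what is estimated. With equal weights, a site with one subject counts as much as a site with twenty, and the visit mean describes the average site instead of the average patient. This matters most for the FJS. It has no pre-operative value and therefore no change from baseline, so its adjusted visit levels are the main model output.

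**Working it through.** **Inputs.** 40 enrolled per group, 36 evaluable, 10% attrition (section 11); up to 8 sites (7.1); 3 visits for the FJS and 4 for the other scores (8.3.2); one knee per subject, because bilateral cases are excluded (7.3). *Assumed, not in the documents:* site sizes, within-subject correlation ρ of 0.3 to 0.7 with compound symmetry, complete data, and equal site weights as the usual LSMeans default.

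**1. The plan's own figure.** No standard error, SD or precision target is given for the PROM models. The only related figure is the group size: 36/(1 − 0.10) = 40, which reproduces.

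**2. Stepwise selection.** If k independent candidates have no effect, the chance that at least one reaches p ≤ 0.1 is 1 − 0.9^k:
- k = 3: 1 − 0.729 = 27%
- k = 6: 1 − 0.531 = 47%
- k = 10: 1 − 0.349 = 65%

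Simulation with 36 to 40 subjects, a fixed site term and three visits agrees (about 27% to 66%). The standard error of a visit mean is then about 1% to 4% too small. Simulated coverage of the nominal 95% interval is about 94% to 95% for a single visit mean and about 93% to 95% for the average over visits.

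**3. Site weights.** Let site s have n_s subjects, with S sites and N = 40.

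- Single visit: SE ratio of the equal-site mean to the patient-weighted mean = sqrt(A), where A = N × Σ(1/n_s)/S².
- Model as specified (additive visit and site, T visits): ratio = sqrt(b × A + w), with b = (1 + (T − 1)ρ)/T and w = (1 − ρ)(1 − 1/T). The site weights act only on the between-subject part.

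Example, sites 12/8/6/5/4/2/2/1: Σ(1/n_s) = 2.825, so A = 40 × 2.825/64 = 1.766 and the single-visit ratio is 1.33. With T = 3 and ρ = 0.5, b = 0.667 and w = 0.333, and the ratio is sqrt(0.667 × 1.766 + 0.333) = 1.23.

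| Assumed site sizes | Single visit | Specified model (T = 3–4, ρ = 0.3–0.7) |
|---|---|---|
| 8 sites of 5, or 4 of 10 | 1.00 | 1.00 |
| 8/7/6/5/5/4/3/2 | 1.10 | 1.05–1.08 |
| 15/12/6/4/3 | 1.20 | 1.10–1.16 |
| 12/8/6/5/4/2/2/1 | 1.33 | 1.17–1.27 |
| 20/8/4/3/2/1/1/1 | 1.63 | 1.34–1.53 |
| 26/5/3/2/1/1/1/1 | 1.78 | 1.43–1.65 |

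For given site weights, the between-subject variance is proportional to the sum of squared weight over n_s. This is smallest when each weight is n_s/N, so under these assumptions patient weighting is never less precise than equal weighting.

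**4. What is not touched.** The model has no visit-by-site term, so a site's contribution is the same at every visit and cancels in any difference between visits. In complete data the standard error of the change is the same under every layout (for example 0.158 residual SDs at ρ = 0.5). FJS contrasts between visits cancel in the same way.

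**The case against.** A reader might infer that the standard errors of the visit means are 20% to 60% too large. The documents do not support that, for four reasons.

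- The standard error of an equal-site mean is correct for that mean. A wider interval than the patient-weighted one reflects the choice of estimand and lower precision, not a miscalculation.
- Equal weighting is an assumption about a software default. The protocol does not state it, and observed margins are not ruled out.
- The size depends on site numbers that the documents do not give. Ratios near 1.6 need one dominant site and several sites of one to three subjects. The single-visit formula also overstates the effect in the model actually specified.
- Stepwise selection works in the opposite direction, making standard errors slightly too small, so it cannot be a joint cause.

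A reader might also infer that no patient-average FJS level will be reported. It will: raw summaries at each visit are planned for every score. Compared with the raw mean, a fixed site term can even reduce the standard error (ratio 0.83 to 0.96 for eight equal sites, if site variance is 0.1 to 0.5 of residual variance).

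It can fairly be said too that section 10 is a brief description, that the SAP is to be finalized before database lock, and that an LSMeans option belongs there. That stands for the weighting. It does not cover the stepwise rule, which section 10.4.2 adopts explicitly. Equal-site weighting is a legitimate target if chosen on purpose; the gap is that no choice is recorded.

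**Conclusion.** The concern holds as a minor, inexpensive improvement.

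The stepwise part does not depend on site sizes. The plan commits to data-driven adjustment in small groups, and the models may differ between scores and groups for no substantive reason. The numerical harm is small, and its exact size depends on how many candidates are tried, which the plan leaves open.

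The site-weighting part is conditional. If sites are weighted equally and recruit unequally, the adjusted visit means are not patient averages and lose precision, within the range tabulated above. If sites recruit evenly, nothing is lost.

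The effect is confined to the adjusted visit means, chiefly those of the FJS. No hypothesis or threshold in the plan attaches to the level of a visit mean.

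**What to change.** In section 10.4.2, carried through to the SAP:

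1. Replace the stepwise rule with one fixed covariate set of age, sex and BMI, used in every PROM model and in both groups.
2. State that visit LSMeans use site weights proportional to the number of subjects (observed margins). If visits are missed, take the weights from subjects and not from records; otherwise subjects with more completed visits count for more.

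The cost is a few sentences, one programming option and up to three degrees of freedom per model. The primary endpoint, sample size and data collection do not change.

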10.4.3 Analysis of Other Endpoint(s)

The analyses for other endpoints (will be carried out separately in the CORI Robotics UKA and CORI Robotics TKA groups.

Leg alignment pre- and post-cementation

Leg alignment pre- and post-cementation will be summarized using descriptive summary characteristics for continuous variables.

Robotics System Time & Cutting Time

Robotic System and cutting times will be summarized using summary statistics for continuous variables. Standard Robotics System and cutting times will be obtained from literature and included in the SAP. The average operating (μ_{11}) and cutting times (μ_{21}) and their commensurate 95% CIs will be summarized compared to the obtained literature-specified (i.e. μ_{10} and μ_{20} respectively) using the t-test.

The following are the possible outcomes, where $i=1$ represents operating time and $i=2$ represents cutting time:

If the lower limit (LL) of the 95% CI for μ_{i1} is $> \mu_{i0}$, then it is concluded that μ_{i1} is significantly greater than μ_{i0} .

If the upper limit (UL) of the 95% CI for μ_{i1} is $> \mu_{i0}$, then it is concluded that μ_{i1} is significantly less than μ_{i0} .

If (LL of 95% CI for $\mu_{i1} \leq \mu_{i0} \leq$ UL for 95% CI of μ_{i1}), then it is concluded that μ_{i1} on-study is comparable to that specified in the literature (μ_{i0}).

All other endpoints will be summarized using the FAS analysis population.

Clinical Protocol

A Prospective, Multi-center, Study to Evaluate the Safety and Effectiveness of REAL INTELLIGENCE™ CORI™ in unicondylar knee arthroplasty (UKA) and total knee arthroplasty (TKA) procedures

Study Number: CORI.2019.07

Version: 6.0, 15/Jan/2024

Page: 59 of 122

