4.2 Literature Summary

A thorough analysis of the literature was performed, and publications were identified that contained clinical outcomes, accuracy measurements, or safety information pertaining to the Robotic Knee Surgical Systems.

Use of the Robotic Knee Surgical Systems was reported in 7 publications with 1 being a prospective study and the remaining 6 being retrospective studies shown in Table 4 1. Three (3) of the studies solely reported on outcomes of the Robotic Knee Surgical Systems, three (3) compared the Robotic Knee Surgical Systems to conventional instruments, and one (1) study compared the Robotic Knee Surgical Systems to conventional instruments, patient specific instrumentation (PSI), and computer-assisted navigation (CAS) systems. All of the studies were for the NAVIO™ Surgical System and reported outcomes for UKA. The data provided in these publications is also applicable to the equivalent CORI Robotics.

Clinical Protocol

A Prospective, Multi-center, Study to Evaluate the Safety and Effectiveness of REAL INTELLIGENCE™ CORI™ in unicondylar knee arthroplasty (UKA) and total knee arthroplasty (TKA) procedures

Study Number: CORI.2019.07

Version: 6.0, 15/Jan/2024

Page: 19 of 122

Table 4-1 Demographic Information for the Robotic Knee Surgical Systems

Primary Author	Year	Robotic System	Indication	Joints (n)	Male (%)	Age, mean±SD (range)	Follow-up, mean±SD
Batailler [39]	2019	NAVIO ¹	UKA	80	33.8	69 ± 9.6 (49-87)	1.64 ± 0.75 years
Battenberg [40]	2019	NAVIO ¹	UKA	128	57.8	64.7 ± 9.6 (45-92)	2.3 years
Canetti [41]	2018	NAVIO ¹	UKA	11	18.0	66.5 ± 6.8 (57-79)	2.87 ± 0.88 years
Gregori [42]	2016	NAVIO ¹	UKA	92	-	-	Periop
Herry [43]	2017	NAVIO ¹	UKA	40	32.5	69 ± 9.6 (49-87)	Periop
Vega Parra [44]	2017	NAVIO ¹	UKA	47	51.0	67 (45-77)	1 years
Sephton [45]	2019	NAVIO ¹	UKA	67	49.0	68 ± 10	Periop
Total				414	49.0%A (33.8-57.8)	66.8A (45-92)	1.14 years (Periop-2.87)

¹ NAVIO™ Surgical System

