10.1 General

Smith Nephew's Global Biostatistics group will conduct the statistical analysis for this study. Unless otherwise stated, all significance tests and hypothesis testing will be two-sided, performed at the 5% significance level. Resulting p-values will be quoted and 95% two-sided confidence intervals

Clinical Protocol

A Prospective, Multi-center, Study to Evaluate the Safety and Effectiveness of REAL INTELLIGENCE™ CORI™ in unicondylar knee arthroplasty (UKA) and total knee arthroplasty (TKA) procedures

Study Number: CORI.2019.07

Version: 6.0, 15/Jan/2024

Page: 55 of 122

will be generated where appropriate. Where data summaries are specified, categorical and ordinal variables will be summarized with frequencies and percentages. Continuous variables will be summarized with the following summary statistics: the number of observations, mean, median, standard deviation, minimum and maximum values.

All statistical comparisons of data would describe the test statistic used as well as its distributional assumptions. For continuous variables, in an event of marked deviation from normality assumption, a commensurate non-parametric test would be used as an alternative thereby eliminating the possibility of violation of normality assumptions. All analyses will be performed using SAS version 9.3 (or a later version).

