11. SAMPLE SIZE JUSTIFICATION

Parratte et al.[53] looked at the effects of postoperative mechanical axis alignment on the survival of TKAs. They found that of the 398 TKAs reviewed in the paper there were 292 (73.4%) which post-operatively were defined as mechanically aligned (i.e. with a mechanical axis of $0^\circ \pm 3^\circ$).

This study is designed to demonstrate superiority in the proportion of TKAs post-operatively defined as mechanically aligned against the reference proportion of 73.4% from above.

Clinical Protocol

A Prospective, Multi-center, Study to Evaluate the Safety and Effectiveness of REAL INTELLIGENCE™ CORI™ in unicondylar knee arthroplasty (UKA) and total knee arthroplasty (TKA) procedures

Study Number: CORI.2019.07

Version: 6.0, 15/Jan/2024

Page: 60 of 122

The proportion of mechanically aligned TKAs using the NAVIO™ Surgical System from a recent analysis was estimated to be 92.1% [54]. If this assumption holds for this study, then the enrollment of 36 knees for each of the two planned study groups (i.e. the CORI Robotics UKA and CORI Robotics TKA) for a total of 72 knees will individually provide approximately 80% power to show that the lower limit of the two-sided 95% confidence interval for the proportion of mechanically aligned TKAs is greater than that obtained from literature. To account for up to a 10% attrition rate in knees enrolled, 40 knees in each group (80 knees combined, 40 UKA, 40 TKA) will be enrolled in the study.

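### Robotics System and cutting times are tested against a literature mean as if it had no sampling error; if the conclusion concerns standard robotic times in general, the false-positive rate exceeds 5% by an amount that the documents do not allow one to fix

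*Combined protocol and SAP*

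**What the plan says.** Section 10.4.3 covers the Robotics System time and the cutting time. The benchmarks are still to be supplied: "Standard Robotics System and cutting times will be obtained from literature and included in the SAP". The CORI means and their "commensurate 95% CIs will be summarized compared to the obtained literature-specified" values, using the t-test. Three outcomes follow, each decided only by where the CORI interval lies relative to the literature value: significantly greater, significantly less, or comparable. No SD, sample size or standard error for the literature value enters the rule.

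These analyses "will be carried out separately in the CORI Robotics UKA and CORI Robotics TKA groups", so two times in two groups make four tests. Section 10.1 sets the level: unless otherwise stated, "all significance tests and hypothesis testing will be two-sided, performed at the 5% significance level".

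The documents give no literature time, source, sample size or SD. The only literature sizes shown for robotic systems are in Section 4.2, Table 4-1, and they are introduced with: "All of the studies were for the NAVIO™ Surgical System and reported outcomes for UKA".

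**The concern.** A standard time taken from published series is a sample mean with its own sampling error. The interval in 10.4.3 carries the error of the CORI mean only. If the reader is meant to learn whether CORI is faster or slower than robotic surgery usually is, the comparison has two sources of error and counts one. It can then reject because the published sample happened to run fast or slow, even when the two true means are equal.

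At stake is a statement that CORI is significantly quicker or slower than standard that rests partly on chance in the benchmark. Correcting the misprinted inequality in the same section, or fixing the benchmark early, would not remove this problem.

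**Working it through.** **Inputs**
- Level: two-sided 5% (Section 10.1).
- CORI sample size per group, n: 36 evaluable, from "the enrollment of 36 knees for each of the two planned study groups"; 40 enrolled, from "To account for up to a 10% attrition rate in knees enrolled, 40 knees in each group" (Section 11).
- Literature sample size, m: not in the documents. Assumed, from 11 to 1000.
- SDs: not in the documents. Assumed equal (ratio r = 1), then r = literature SD / CORI SD = 0.5 and 2.
- Lower-side rule: Section 10.4.3 prints significantly less when the upper limit is *above* the benchmark. The check reads it as *below*, which is evidently intended.

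**Step 1. The plan's own figure.** With the benchmark a fixed constant, the level is 2·P(t with n−1 df > c), where c is the 97.5% point. For n = 36, c = 2.030; for n = 40, c = 2.023. Both give 5.0%, so the stated level reproduces.

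**Step 2. Let the benchmark be a mean of m cases.** With equal true means, the variance of (CORI mean − literature mean) is σ²/n + r²σ²/m = (σ²/n)(1 + r²n/m). The planned statistic divides by CORI's standard error only. For normal data it is therefore k times a t variable with n−1 df, where k = √(1 + r²n/m). The rejection rate is 2·P(t with n−1 df > c/k). Since k > 1 for any finite m, the rate is always above 5%.

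Example, n = 40, m = 40, r = 1: k = √2 = 1.414; c/k = 2.023/1.414 = 1.430; rate = 16.1%.

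**Step 3. Range over m, equal SDs**

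| m | n = 36 | n = 40 |
|---|---|---|
| 11 | 33% | 35% |
| 40 | 15.0% | 16.1% |
| 47 | 13.6% | 14.5% |
| 67 | 11.1% | 11.8% |
| 80 | 10.1% | 10.7% |
| 92 | 9.4% | 9.9% |
| 128 | 8.2% | 8.5% |
| 414 | 6.0% | 6.1% |
| 1000 | 5.4% | 5.4% |

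Simulation with 200,000 runs agrees: for n = 40 it gives 16.1% at m = 40 and 8.5% at m = 128.

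**Step 4. Unequal SDs, m = 40.** With r = 0.5 the rate is 7.5% (n = 36) or 7.8% (n = 40). With r = 2 it is 35% or 37%.

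**Step 5. What Table 4-1 can say about m.** It lists seven series: 80, 128, 11, 92, 40, 47 and 67 joints. Section 4.2.1 says that the 11- and 40-joint series probably share patients with the 80-joint series, and leaves them out of the total: 80 + 128 + 92 + 47 + 67 = 414. That leaves five independent series of 47 to 128 joints, three of them with 80 or fewer. All are UKA, and none is identified as a source of times.

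**Step 6. Does the remedy work?** A Welch two-sample test that carries the literature error gives simulated rates of 4.98% (n = 36, m = 40), 4.93% (n = 40, m = 40) and 5.06% (n = 40, m = 128), with equal SDs.

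**The case against.** The strongest reply is that the test is correct for the hypothesis as written. Section 10.4.3 compares a CORI mean with a literature-specified value. If that value is a fixed benchmark, the level is exactly 5% and nothing in Section 10.1 is breached. The primary endpoint is handled in the same way, against a fixed 73.4%. This stands. However, 10.4.3 calls the values standard times from literature and does not declare a performance goal, so a reader is likely to take a significant result as a statement about robotic surgery in general.

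Second, the size is unknown. A reader might infer from Table 4-1 that the rate is roughly 9–16%. That holds only for about 36 to 113 literature cases with equal SDs, and neither condition is in the documents. A benchmark pooled over 414 joints would give about 6%. Nor can one say that five of seven series are small, because two of those five overlap with a third. No TKA series is listed, so the table gives no guide to size for half of the tests.

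Third, these rates do not describe the rule as printed. Taken literally, the reversed inequality gives some significant verdict in about 97.5% of null cases with a fixed benchmark, and in 92–96% with m from 40 to 128. That error is larger and must be corrected first; the present point is what remains afterwards.

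Fourth, the synopsis labels these endpoints exploratory, Section 5.3 aims only to determine the times, and Section 5.4 says that no claims are to be confirmed. This limits the importance of the point but does not remove it, because 10.4.3 still prescribes formal significance conclusions.

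**Conclusion.** The point holds conditionally. If the conclusion is meant to be about standard robotic times and not about one fixed number, the planned test has a false-positive rate above 5% for any finite literature sample. The direction needs no assumption about the literature sample size. The size does: with equal SDs, n of 36 to 40 and the inequality corrected, it runs from 5.4% at m = 1000 to 33–35% at m = 11, and is about 8–15% for series of 47 to 128 cases. The SD ratio matters as much: at m = 40 the rate runs from 7.5% to 37% as the ratio goes from 0.5 to 2.

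The documents do not support a single inflated rate as a property of the plan, a statement that Section 10.1 is contradicted, or any sizing for TKA. This is a minor improvement to an exploratory analysis. It leaves the primary conclusion untouched.

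**What to change.** In Section 10.4.3 and the SAP:

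1. Record the source, mean, SD and n of each time benchmark, separately for UKA and TKA.
2. Replace the one-sample t-test by a Welch comparison computed from summary statistics, with a 95% confidence interval for the CORI mean minus the literature mean.
3. Where SD or n is unavailable, or the value is intended as a fixed benchmark, say so. Report the CORI mean and interval beside it, and do not conclude that CORI is significantly faster or slower than standard robotic surgery.
4. Correct the upper-limit inequality at the same time.

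The cost is some SAP wording and one formula. The price is a wider interval and fewer significant results. Welch does not make unlike times comparable: Section 9.2.7 defines both times by transitions in the CORI log, and published times with other start and stop points would still bias the difference. The start and stop definitions should therefore be recorded with each benchmark.
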